### **13.2 Definition of SAE**

Any untoward medical occurrence that, at any dose, results in death; is life threatening (ie, an event in which the patient was at risk of death at the time of the event; it does not refer to an event that hypothetically might have caused death if it were more severe); requires inpatient hospitalization or prolongation of existing hospitalization; results in persistent or significant disability/incapacity; or is a congenital anomaly/birth defect. Important medical events that may not result in death, be life-threatening, or require hospitalization may be considered serious when, based upon appropriate medical judgment, they may jeopardize the patient or subject and may require medical or surgical intervention to prevent one of the outcomes listed in this definition. Examples of such medical events include allergic bronchospasm requiring intensive treatment in an emergency room or at home, blood dyscrasias or convulsions that do not result in inpatient hospitalization, or the development of drug dependency or drug abuse.

Please note that SAEs that occur at any time between the signing of the ICF up to the first dose of study treatment, must be reported (in addition to SAEs that occur after the first dose of study treatment).

Hospitalizations for elective surgery or other medical procedures that are not due to an AE are not considered SAEs. A hospitalization meeting the regulatory definition for 'serious' is any inpatient hospital admission that includes a minimum of an overnight stay in a health care facility greater than 24 hours or results in a prolongation of a current hospitalization. An emergency room visit is not considered a hospitalization unless it results in an official admission to the hospital.

Progression of the malignancy (including fatal outcomes) should not be reported as an SAE during the study or within the safety reporting period. Sudden and unexplained death should be reported as an SAE. If there is any uncertainty about a finding being due solely to progression of malignancy, the finding should be reported as an AE or

SAE, as appropriate.

Progression of the malignancy (including fatal outcomes) if documented per IMWG criteria for progression of MM (see Appendix 4), should not be reported as an SAE during the study or within the safety reporting period (see below).

The Investigator will record and document all SAEs occurring from the signing of the ICF until at least 30 days after the patient has stopped study treatment. All SAEs must be reported on the SAE Report Form in addition to being recorded in the eCRF. The original SAE report form must be retained in the Investigator's site file.

All applicable sections of the form must be completed in order to provide a clinically thorough report. The Investigator must assess and record the relationship of each SAE to study treatment and complete the SAE Report Form. Key data elements required for expedited reporting will follow ICH E2A standards (Clinical Safety Data Management: Definitions and Standards for Expedited Reporting).

### **13.2.1 Reporting of SAE to IRB**

All SAEs occurring on this study will be reported to the IRB according to the IRB policy, which can be accessed via the following link:

[http://researchintegrity.weill.cornell.edu/forms\\_and\\_policies/forms/Immediate\\_Reportin \\_Policy.pdf](http://researchintegrity.weill.cornell.edu/forms_and_policies/forms/Immediate_Reportin _Policy.pdf).

### **13.2.2 Reporting of SAE to FDA**

The Investigator must report any suspected adverse reaction or adverse reaction to study treatment that is both serious and unexpected. Unexpected fatal or life-threatening suspected adverse reactions represent especially important safety information and must be reported to FDA as soon as possible but no later than 7 calendar days following the sponsor's initial receipt of the information.

- i. death,
- ii. a life-threatening adverse event,
- iii. in-patient hospitalization or prolongation of existing hospitalization,
- iv. a persistent or significant incapacity or substantial disruption of the ability to conduct normal life functions, or
- v. a congenital anomaly or birth defect

Important medical events that may not result in death, be life-threatening, or require hospitalization may be considered serious when, based upon appropriate medical judgment, they may jeopardize the patient or research subject and may require medical or surgical intervention to prevent one of the outcomes listed as serious

### **13.2.3 Reporting of SAE to Karyopharm Therapeutics, Inc.**

Every SAE, regardless of the causal relationship to the study treatment, occurring after the patient has signed informed consent, until at least 30 days after the patient has stopped study treatment, must be reported to the Karyopharm Pharmacovigilance Department within 24 hours of learning of its occurrence. The investigational site personnel must use the SAE Report Form provided by Karyopharm for reporting any SAE to the Karyopharm Pharmacovigilance Department, including:

- Protocol number
- Site and/or Investigator's number
- Patient's number
- Brief description of the event
- Resolution date and time, if the event resolved
- Any medication administered to treat the event
- Investigator's assessment of the SAE's relationship to investigational product
- Outcome of the event on the date of report

Upon completion, the SAE Report Form must be immediately emailed or faxed to:

Pharmacovigilance Department

Karyopharm Therapeutics Inc.

Email: [[contact]](mailto:[contact])

[contact] (USA)

[contact] (Germany)

Any SAE observed after the 30-day follow-up period should only be reported to Karyopharm if the Investigator suspects that the SAE has a causal relationship to study treatment. Recurrent episodes, complications, or progression of the initial SAE must be reported as follow-up to the original episode within 24 hours of the Investigator receiving the follow-up information.

An SAE should be followed until its resolution or until it is judged to be permanent, and assessment should be made at each visit (or more frequently, if necessary) of any changes in severity of the event, the suspected relationship to the study treatment, the interventions required to treat the event, and the outcome.

#### **13.2.4 Reporting of SAE to WCM by Sub-sites**

Within 24 of the Investigator's knowledge of the event, participating sites must report SAE to WCM by sending the following forms via email to **[contact]**:

WCM SAE Cover Sheet

- Karyopharm SAE form
- Form FDA 3500A for Mandatory Reporting (MedWatch)  
<https://www.fda.gov/downloads/AboutFDA/ReportsManualsForms/Forms/UCM048334.pdf>

The SAE should be reported to the participating site's institutional regulatory board (IRB), as per institutional guidelines. Proof of submission and IRB acknowledgment should be sent via email to **[contact]** when received.

WCM (Sponsor-investigator) is responsible for reporting the SAE to the Karyopharm Therapeutics, the FDA, and any other applicable regulatory agencies.

#### **13.3 AE/SAE Follow Up**

All SAEs and AEs reported during this study will be followed until resolution or until the investigator confirms that the AE/SAE has stabilized, and no more follow-up is required. This requirement indicates that follow-up may be required for some events after the subject discontinues participation from the study, as outlined in the Follow Up Phase above.

#### **13.4 Time Period and Frequency for Event Assessment and Follow Up**

The occurrence of an adverse event (AE) or serious adverse event (SAE) may come to the attention of study personnel during study visits and interviews of a study participant presenting for medical care, or upon review by a study monitor.

All AEs including local and systemic reactions not meeting the criteria for SAEs will be captured on the appropriate case report form (CRF). Information to be collected includes event description, time of onset, clinician's assessment of severity, relationship to study treatment (assessed only by those with the training and authority to make a diagnosis), and time of resolution/stabilization of the event. All AEs occurring while on study must be

documented appropriately regardless of relationship. All AEs will be followed to adequate resolution.

Any medical condition that is present at the time that the participant is screened will be considered as baseline and not reported as an AE. However, if the study participant's condition deteriorates at any time during the study, it will be recorded as an AE.

Changes in the severity of an AE will be documented to allow an assessment of the duration of the event at each level of severity to be performed. AEs characterized as intermittent require documentation of onset and duration of each episode.

The investigator or research nurse will record all reportable events with start dates occurring any time after informed consent is obtained until 7 (for non-serious AEs) or 30 days (for SAEs) after the last day of study participation. At each study visit, the investigator will inquire about the occurrence of AE/SAEs since the last visit. Events will be followed for outcome information until resolution or stabilization.

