## **2.4 Risk/Benefit Assessment**

### **2.4.1 Known Potential Risks**

Measures will be taken to ensure the safety of the patients participating in this trial, including the use of stringent inclusion and exclusion criteria and close monitoring. If toxicities are encountered, adjustments will be made to the study treatment as detailed in the sections below. All adverse events (AEs) and serious adverse events (SAEs) will be recorded during the trial and for up to 30 days after the last dose of study treatment or until the initiation of another anticancer therapy, whichever occurs first.

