#### **12.4.2 Analysis of Secondary Endpoints**

Safety analyses will be performed using data available from all patients who receive  $\geq 1$  dose of the study treatment. Adverse Events (AEs) will be coded using the Medical Dictionary for Regulatory Activities (MedDRA) dictionary and displayed in tables and listings using System/Organ/Class (SOC) and Preferred Term. Analyses of AEs will be performed for those events that are considered to be treatment emergent AEs (TEAEs), defined as any AE with onset or worsening of a pre-existing condition on or after the first administration of study medication through 30 days following last dose or any event considered drug-related by the Investigator through the end of the study. AEs with partial dates will be assessed using the available date information to determine if treatment-emergent; AEs with completely missing dates will be assumed to be treatment-emergent.

AEs will be summarized by patient incidence rates. In all tabulations, a patient may contribute only once to the count for a given AE preferred term. The number and percentage of patients with TEAEs will be summarized, as well as the number and percentage of patients with TEAEs assessed by the Investigator as at least possibly related to treatment. The number and percentage of patients with any Grade  $\geq 3$  TEAE will be tabulated in the same manner. In the event that a patient experiences repeated episodes of the same TEAE, the event with the highest severity and/or strongest causal relationship to study treatment will be used for purposes of tabulations. Serious AEs (SAEs) will also be tabulated. No formal hypothesis-testing analysis of AE incidence rates will be performed.

All AEs (treatment emergent and post-treatment) will be listed in patient data listings. Separate by-patient listings will be provided for the following: patient deaths, SAEs, and AEs leading to withdrawal.

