### **13.1.3 Recording of Adverse Events**

All AEs that begin or worsen after the patient has provided informed consent will be recorded on the AE eCRF, regardless of whether dosing with study drug has commenced. AE monitoring should be continued for at least 30 days following the last dose of study treatment (i.e., through 30 days following last dose or until resolution or through the end of the study for events considered related to study treatment by the Investigator). AEs (including laboratory abnormalities that constitute AEs) should be described using a diagnosis whenever possible, rather than individual underlying signs and symptoms. When a clear diagnosis cannot be identified, each sign or symptom should be recorded as a separate AE.

The Investigator should ask the patient non-leading questions to determine if AEs occur during the study. AEs may also be recorded when they are volunteered by the patient, or through physical examination, laboratory tests, or other clinical assessments.

An AE should be followed until its resolution or until it is judged to be permanent, and assessment should be made at each visit (or more frequently, if necessary) of any changes in severity of the event, the suspected relationship to the study treatment, the interventions required to treat the event, and the outcome.

Laboratory abnormalities that constitute an AE in their own right (i.e., are considered to be clinically significant, induce clinical signs or symptoms, require concomitant therapy, or require changes in study treatment), should be recorded on the Adverse Events eCRF.

Whenever possible, a diagnosis, rather than a symptom should be provided (e.g., anemia instead of low hemoglobin). Laboratory abnormalities that meet the criteria for an AE should be followed until they have returned to baseline (at screening) or an adequate explanation of the abnormality is identified. When an abnormal laboratory or test result corresponds to a sign/symptom of an already reported AE, it is not necessary to separately record the laboratory/test result as an additional event.

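### The adverse-event recording rules in 2.4.1 and 13.4 do not match the analysis window in 12.4.2, and the two causality categories in 13.1.2 cannot fill its related-event table

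*Combined protocol and SAP*

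**What the plan says.** **Analysis window.** Section 1.2.5 lists one secondary endpoint, the frequency of participants with AEs. Section 12.4.2 analyses it on treatment-emergent AEs (TEAEs), which run from first dose "through 30 days following last dose or any event considered drug-related by the Investigator through the end of the study". It makes no distinction by seriousness and has no cut at new therapy.

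**Recording rules.**
- Section 13.1.3 agrees with 12.4.2: "AE monitoring should be continued for at least 30 days following the last dose of study treatment", with a longer period for related events.
- For SAEs, 13.2 requires the investigator to document "all SAEs occurring from the signing of the ICF until at least 30 days after the patient has stopped study treatment". Section 13.2.3 covers the same period for reports to the drug supplier: "until at least 30 days after the patient has stopped study treatment, must be reported to the Karyopharm Pharmacovigilance Department within 24 hours".
- Section 2.4.1 differs: "All adverse events (AEs) and serious adverse events (SAEs) will be recorded during the trial" and then "for up to 30 days after the last dose of study treatment or until the initiation of another anticancer therapy, whichever occurs first".
- Section 13.4 differs again, recording events "until 7 (for non-serious AEs) or 30 days (for SAEs) after the last day of study participation".

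**Contacts after treatment.** The 30-day contact has a window of ±7 days in the Schedule (Table 2) and 6.1.3.1, but +7 days in 7.10.1. Section 7.10.1 names only AEs still open at the end-of-treatment (EoT) visit, whereas the Schedule and 6.1.3.1 list AEs without restriction. The 3-monthly contacts carry no AE item in the Schedule, its footnote 5b, 6.1.3.2 or 7.10.2.

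**Causality.** Section 13.1.2 has two categories. Related requires a definitive link in time and that study treatment explains the event better than anything else. Not related requires that a causal link is not reasonably possible, or that something else explains the event sufficiently. Section 12.4.2 calls for a table of TEAEs judged at least possibly related, and for repeated events it keeps the one with the highest severity, the strongest causal link, or both.

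**The concern.** The protocol states several end points for AE recording and does not say which governs. Events never recorded cannot be restored at analysis, and the protocol summary names two enrolling sites, which could follow different sections. The early cut in 2.4.1 is a realistic case: under 7.9 treatment may continue until progression, and the 30-day contact in 7.10.1 itself asks which antineoplastic therapies have been used since study treatment stopped.

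The causality wording raises a separate problem. An investigator who thinks a causal link is reasonably possible but not definitive, and sees no sufficient alternative, has no category to tick. That affects the related-TEAE table. It also affects the extension of the TEAE window to late drug-related events, because entry to that extension depends on the same judgement.

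**Working it through.** The plan gives no figure to reproduce, so the rules are put on one scale: days after last dose. The target from 12.4.2 is days 1 to 30 for any AE.

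**Section 2.4.1 (AEs and SAEs).** Let d be the day on which another anticancer therapy starts. Days lost = max(0, 30 − d). The documents give no distribution for d, so these values are assumptions:
- d = 7: 30 − 7 = 23
- d = 14: 30 − 14 = 16
- d = 21: 30 − 21 = 9
- d ≥ 30: 0

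Section 2.4.1 also has no extension for drug-related events after day 30, which 12.4.2 counts.

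**Section 13.4, non-serious AEs.** Let P be the day on which study participation ends. Recording stops at P + 7, and days lost = max(0, 30 − (P + 7)). The EoT visit falls up to 14 days after last dose (6.1.2.7), and follow-up lasts 12 months (6.1.3.2, taken here as 365 days from last dose).

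| Reading of the anchor | P | Stops on day | Days lost |
|---|---|---|---|
| Last dose | 0 | 7 | 23 |
| Latest EoT visit | 14 | 21 | 9 |
| Earliest 30-day contact under ±7 | 23 | 30 | 0 |
| End of 12-month follow-up | 365 | 372 | 0 |

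**Section 13.4, SAEs.** Recording stops at P + 30, which is never before day 30. Days lost: 0 on every reading.

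**Which reading of 13.4?** Section 3.4 treats a participant as complete after the last follow-up assessment, and 8.1 says that stopping treatment is not leaving the study. Both favour the last row. The shorter readings also have some textual basis: 13.3 speaks of follow-up after a subject has discontinued participation, and 7.8.14 and Table 4 describe taking patients off the study for toxicity.

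**30-day contact.** Under ±7 the earliest contact is day 30 − 7 = 23, so that contact cannot itself cover days 24 to 30 (7 days). Under +7 the earliest is day 30, and 0 days are left uncovered.

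**Causality.** Consider an event that is (a) reasonably possible, (b) not definitive and (c) without a sufficient alternative explanation. By (b) it is not Related. By (a) and (c) it is not Not related. The two categories are therefore not exhaustive. Treating Related as the at-least-possibly-related group would produce a table, but one that counts only definitive events. The protocol uses a reasonable-possibility standard elsewhere: in 13.1 for a suspected adverse reaction, and in 14.1 to explain possibly related.

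**The case against.** The strongest reply is that a sound rule already exists. Section 13.1.3 is the section on recording AEs and agrees with 12.4.2, 13.2 and 13.2.3 set the same minimum for SAEs, and 2.4.1 is background text. Section 13.4 also says that AEs occurring on study are documented regardless of relationship, that AEs are asked about at each study visit since the previous one, and that events may surface through medical care or monitoring. The post-treatment tail is short, too. With about 10 months of treatment (protocol summary, about 304 days), 30 days are 30/334 = 9% of the TEAE window, and the worst-case 23 days are 23/334 = 7%.

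Much of this stands. A reader might infer that 13.4 loses most of the 30-day window for non-serious AEs. The documents do not support that: it needs the less-favoured reading of the anchor. Where a patient withdraws consent at last dose, no wording recovers the later days. A reader might also infer that late drug-related events go uncollected. That is too strong given the general inquiry in 13.4; what is missing is an AE item at the 3-monthly contacts.

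The reply does not remove the conflict. Section 2.4.1 states what will be recorded and gives no precedence to 13.1.3, and the anchor in 13.4 remains undefined. Nothing in the reply supplies the missing causality category.

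**Conclusion.** The point holds as a mismatch of text that should be corrected before the safety tables are relied on.

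- **2.4.1** is narrower than 12.4.2 whenever new therapy starts before day 30, for AEs and SAEs alike: 23, 16 or 9 days for assumed starts on day 7, 14 or 21. It also omits late drug-related events.
- **13.4** loses 0 days on the reading that 3.4 and 8.1 favour, and 9 to 23 days of non-serious AEs if a site reads the anchor as EoT or last dose. SAEs are not short on any reading.
- **The 30-day contact**, at its earliest under ±7, leaves days 24 to 30 outside its own reach.
- **The related-TEAE table** cannot be filled as worded.

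The consequences are limited. In the tables "a patient may contribute only once to the count for a given AE preferred term", so a missed event changes a term's count only if that patient had not already had the term. No hypothesis test is planned on AE rates, all-cause AE frequency within 30 days does not depend on relatedness, and the response-rate test is unaffected. It would be wrong to infer that AE rates are biased in a known direction: the documents do not say how many AEs fall in the affected days or in the causality gap.

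**What to change.** 1. **Recording.** Align 2.4.1 and 13.4 with 13.1.3 and 12.4.2: record all AEs and SAEs through at least 30 days after last dose, whether or not new therapy starts, and drug-related events to the end of the study. Anchor 13.4 on last dose. Keep the requirement in 13.1.6 to capture all second primary malignancies, without a time or relatedness limit.
2. **Contacts.** Use one window for the 30-day contact that does not close before day 30; the +7 days already in 7.10.1 does this. Have 7.10.1 ask about new or worsened AEs as well as open ones. Add a question on related AEs at the existing 3-monthly contacts (Schedule, footnote 5b, 6.1.3.2, 7.10.2).
3. **Causality.** For the safety tables and the late-event extension in 12.4.2, make the categories in 13.1.2 exhaustive and consistent with 12.4.2, for example by using the reasonable-possibility wording of 13.1 for the analysis category. Relatedness also triggers dose, off-treatment, new-cycle and stopping rules in 7.7.1, 7.8.14 and 15. The sponsor must reconcile those passages with whatever definition is adopted; no clinical threshold is proposed here.

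The cost is protocol wording, minor case report form wording and one added question at contacts that already exist, with no new visit. Reported related-AE rates may be somewhat higher.

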## **14. Unanticipated Problems Involving Risks to Subjects or Others**

### **14.1 Definition of Unanticipated Problems Involving Risks to Subjects or Others (UPIRTSO)**

The Office for Human Research Protections (OHRP) considers unanticipated problems involving risks to participants or others to include, in general, any incident, experience, or outcome that meets all of the following criteria:

- Unexpected in terms of nature, severity, or frequency given (a) the research procedures that are described in the protocol-related documents, such as the Institutional Review Board (IRB)-approved research protocol and informed consent document; and (b) the characteristics of the participant population being studied;
- Related or possibly related to participation in the research ("possibly related" means there is a reasonable possibility that the incident, experience, or outcome may have been caused by the procedures involved in the research); and
- Suggests that the research places participants or others at a greater risk of harm (including physical, psychological, economic, or social harm) than was previously known or recognized.

